8.1.3 Other study parameters

Clinical parameters at intake: age, body weight, comorbidity.

Dietary parameters: weekly lycopene food content estimated by weekly food questionnaires.

8.2 Randomisation, blinding and treatment allocation

10 study subjects randomised for study scheme AB versus BA (cross-over) by blinded draw of 10 tickets by an independent statistician. The 10 study subjects will be randomized at once, before the start of the study.

8.3 Study procedures

Participants will be randomized into the study scheme AB versus BA (cross-over). One week before the intervention a food frequency questionnaire will be distributed to participants. Group A will take 40mg lycopene (2,5 pills of food supplement Vitabiotics Ultra Lycopene 15mg, potent extract). Group B will take 250 ml of tomato soup (matching with 40mg lycopene) with 20ml olive oil. Wash out period of 3 weeks, after which the identical procedure takes place including questionnaires, but group A and B changed (cross-over).

Blood draws are taken on indicated time points (before intervention, 1, 3, 6, 12, 24, 48 and 72 hours after intervention) in standard vacutainers (BD Vacutainer; Becton, Dickinson and Company). For the first blood draws (before intervention and 1-24 hours

after the intervention) all participants will be given an infusion needle for 26 hours. Blood draws after 48 and 72 hours will be done by direct venapunction. Next, the tubes are centrifuged at 3000g for 10 minutes at 4 °C (Sigma 4-16K; Sigma-zentrifugen). Plasma samples are immediately put on dry ice for rapid freezing. At the end of each test day, the plasma samples are stored at -80 °C until further analysis.

Standard liquid-chromatography-based technology for the analysis of carotenoids and similar structures including lycopene. Plasma carotenoids, including retinol, alpha- and beta-carotene, beta-cryptoxanthin, lutein, lycopene, tocopherols and zeaxanthin, are determined using ultra-pressure liquid chromatography coupled to diode array detection (UPLC-DAD). In short, 375 µL plasma is denatured using ethanol in the presence of the internal standard retinyl acetate. The carotenoids are subsequently extracted using 0.01% w/v butylated hydroxytoluene in hexane. The extracts are dried under nitrogen in a TurboVap evaporator (Biotage, Uppsala, Sweden) at 35 °C, reconstituted in acetonitrile, and transferred to a LC vial. LC analysis is performed on a Acquity H-class UPLC coupled to an Acquity PDA eLambda detector (Waters, Etten-Leur, the Netherlands) using an Acquity UPLC HSS T3 column (Waters). Gradient elution is performed using a mixture of acetonitrile-dichloromethane-methanol (ratio 85:5:10) containing 0.1% ammonium acetate (eluens A) and ULC-MS grade water (eluens B) with a constant flow of 400 µL/min and a runtime of 30 min. The detector is set at 292, 325 and 450 nm. Concentrations are calculated using a 6-point calibration curve. A pooled plasma sample is analyzed in duplicate in each analytical batch to monitor the quality of the analyses.

An extensive Food Frequency Questionnaire (FFQ) will be used to assess the participants' habitual diet of the previous month. This extensive FFQ was validated for energy, macronutrients, and a number of vitamins [14-17] and administered online with the self-administered Dutch FFQ-tool™ [18], one week prior to the intervention. Participants indicate the frequency of consumed food items by selecting answers ranging from 'not consumed' to '7 days per week' and portion sizes can be estimated using natural portions and commonly used household measures. The Dutch Food Composition Database (i.e., NEVO) will be used to calculate energy and nutrient content of foods.

During the intervention, participants will report their food intake in a smartphone-based food diary on the first day of the intervention and the two following days. For this purpose, Traqq® will be used, an ecological momentary dietary assessment app [19]. In the morning, participants will receive a notification on their smartphone from Traqq®, inviting them to report their food intake during that day. Participants report their food intake by

clicking on the notification or opening the app. Next, participants can select consumed foods from an extensive food list based on the Dutch Food Composition Database. Subsequently, participants are prompted to report quantity and eating occasion, i.e., breakfast, lunch, dinner, snack. Quantity can be reported in household measures (e.g., spoon, cup), standard portion sizes (e.g., small, large) or amount in grams. Traqq® also contains a “My dishes” feature where participants can enter all ingredients of a recipe and the portion of the dish consumed, with yield and retention factors automatically being taken into account. The “My Dishes” feature can also be used to create frequently consumed product combinations (e.g., daily breakfast), which simplified reporting of these items and decreases (mis)calculation errors.

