1. INTRODUCTION AND RATIONALE

Dietary study in Prostate cancer: Men with prostate cancer (PCa) often ask if the (composition of) their diet may contribute to the suppression of their tumor. There is indirect epidemiological evidence that diet, especially antioxidants like lycopene, are beneficial for an advantageous course of PCa [1]. Lycopene is a non-provitamin A carotenoid that exhibits several health benefits. Epidemiological data support a correlation between lycopene intake and the attenuation of several chronic diseases, including certain types of cancers and cardiovascular diseases. It is currently unknown whether the beneficial effects are from the native structure of lycopene or its metabolic derivatives [2].

Scientific proof for the impact of dietary interventions on PCa growth is extremely difficult to provide, as the natural course of PCa from the time of diagnosis is frequently over 20 years. In dietary studies many confounders are present, therefore dietary studies also need extreme large populations. Furthermore, the biochemical parameters needed to study lycopene concentrations in blood do not have defined normal values: SNPs in *BCO1* and other genes may modulate human plasma and prostate tissue responses to dietary lycopene intake. These individual genetic variants related to carotenoid metabolism may partially explain heterogeneous human blood and tissue responses and may be critical covariates for population studies and clinical trials [3]. On top of that, intestinal absorption is promoted by co-consumption of fat [2], and 10 gram of olive oil has been identified as an optimal dose for lycopene uptake. The way lycopene itself is offered appears to be less of importance, as there was no difference of plasma concentration observed between well processed dietary and artificial in-tablet servings of lycopene [4].

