Study design: We have chosen lycopene as it is related to PCa growth, it can be used as a dietary intervention, and it is measurable reproducibly in food and in body fluids. Here we study the lycopene plasma concentration dynamics after a single dose consumption in volunteers in a Dutch setting (which differs from the geographic and environmental setting and life-style in the above mentioned studies). This is to obtain the necessary information on technology, logistics, and food products needed to conduct the follow-up study (METC 2017-389) in cancer patients. Once we have proven that a measurable response can be obtained in healthy volunteers in a Dutch population, that the assay is available and robust, and in line with food consumption as evaluated by validated food questionnaires, we will incorporate that parameter (lycopene) in the current randomised study for men with PCa and undergoing treatment or have undergone treatment in the past in which three dietary interventions are given and compliance to the intervention is currently measured by food intake questionnaires (METC 2017-389).

Here we test plasma lycopene as a candidate compliance marker for that purpose. This is based on the assumption that in Dutch participants the plasma level of lycopene might be comparable to the Swiss population literature, that a single dose response to 40 mg lycopene in combination with oil will provide a measurable response of plus 10 % in individuals, and that a concentration between 1000-1500 nmol/l is appreciated by patients and caregivers as the optimal lycopene plasma concentration to be accomplished long term (1-3 months).

Dietary interventions should always be analysed against the background of the normal individual diet. Therefore, to evaluate the lycopene intervention and related marker, it is

crucial to take the participant's habitual diet, as well as actual food intake during the intervention into account [6].

Research questions:

- 1) Can a plasma lycopene concentration serve as a response parameter after a single dose of dietary lycopene.

We will measure plasma carotenoid concentrations (including lycopene) in response to a single dose dietary intervention with lycopene-rich food or a lycopene tablet in a cross-over study design.

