Plasma lycopene concentrations show variation between individuals, and within individuals. It is unknown if and how much a single dietary intervention with lycopene from lycopene-rich vegetables like tomatoes alters the plasma concentration, and therefore can be used as a compliance marker.

As the bioavailability and plasma kinetics of lycopene is known to a limited extend (see studies above), a scheme for plasma determinations is followed according to previous marker (GABA, also found in tomatoes, serving as an exemplary study design) research from the same Wageningen group, including a wash out period of at least two weeks between interventions in the cross-over design [7].

- 2) Is a tablet lycopene with equivalent lycopene content as effective as a single dose dietary intervention regarding the change of plasma lycopene concentration?

Previous studies suggest equivalence, which might be of interest for consumers/patients.

- 3) Is the prior food consumption of individuals, as measured by dietary questionnaires, related to the plasma lycopene levels before and after lycopene intervention?

If an existing individual high intake of lycopene as analysed by a validated questionnaire would result in a high standard plasma lycopene concentration, or little response on single dose lycopene consumption, the subject might exclude for further supplementary lycopene consumption and life style changes.

Intervention: We have chosen a single dose of 40 mg lycopene as an intervention based on the following. Previously, in a dose escalating study to 90 mg lycopene daily in men with Research protocol

recurrent PCa after primary treatment, no effects were seen on the level of PSA, in contradiction to two studies conducted in men with metastatic PCa [8]. Also in high doses maintained for several weeks no toxicity was observed, while lycopene plasma levels corresponded with dietary dose. For chronic use, the daily dose of 30 mg is recommended based on a large review [9].

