Lycopene belongs to the chemical family of carotenoids that can be found in intensely coloured fruits and vegetables, like tomatoes. The uptake from the alimentary tract is increased by heating the natural present lycopene, initiating a chemical conversion from a trans to a cis-form [10]. Uptake of lycopene and its geometrical isomers is greater from heat-processed than from unprocessed tomato juice in humans [10]. The addition of oils also are reported to have a beneficial influence [11]. Lycopenes are absorbed in the gut, and transported in chylomicrones because of their lipophylic nature [12]. Their exact biological action is still unknown, but regarded to be an antioxidant.

Various dietary interventions have been applied previously for the study on bioavailability of lycopene. The lycopene content in 200g of tomato soup equals ca.33 mg of lycopene. Most experimental studies aim to provide 40 mg lycopene whether in a carotene-rich diet, whether by pill-form (supplement), in combination with a minimum of 10 g of fat [2].

Assay: Standard liquid-chromatography-based technology for the analysis of carotenoids and similar structures including lycopene. Plasma carotenoids, including retinol, alpha- and beta-carotene, beta-cryptoxanthin, lutein, lycopene, tocopherols and zeaxanthin, are determined using ultra-pressure liquid chromatography coupled to diode array detection (UPLC-DAD). In short, 375 µL plasma is denatured using ethanol in the presence of the internal standard retinyl acetate. The carotenoids are subsequently extracted using 0.01% w/v butylated hydroxytoluene in hexane. The extracts are dried under nitrogen in a TurboVap evaporator (Biotage, Uppsala, Sweden) at 35 °C, reconstituted in acetonitrile, and transferred to a LC vial. LC analysis is performed on a Acquity H-class UPLC coupled to an Acquity PDA eLambda detector (Waters, Etten-Leur, the Netherlands) using an Acquity UPLC HSS T3 column (Waters). Gradient elution is performed using a mixture of acetonitrile-dichloromethane-methanol (ratio 85:5:10) containing 0.1% ammonium acetate (eluens A) and ULC-MS grade water (eluens B) with a constant flow of 400 µL/min and a runtime of 30 min. The detector is set at 292, 325 and 450 nm. Concentrations are calculated using a 6-point calibration curve. A pooled plasma sample is analyzed in duplicate in each analytical batch to monitor the quality of the analyses.

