2. OBJECTIVES

Primary Objective:

To determine whether a plasma lycopene concentration can serve as a response parameter after a single dose of dietary lycopene.

Secondary Objectives:

1. To determine if a food supplement tablet lycopene with equivalent lycopene content compared to a single dose dietary intervention provides identical plasma lycopene concentration responses compared to the dietary intervention.
2. To determine the influence of prior food consumption, as measured by dietary questionnaires, on plasma lycopene levels before and after lycopene intervention.

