5. TREATMENT OF SUBJECTS

5.1 Investigational product/treatment

Intervention 1: 40 mg lycopene (i.e. 2.5 food supplement pills of Vitabiotics Ultra Lycopene 15mg, potent extract). Tablets contain 430mg Tomato Extract which provides 15mg pure Lycopene, no artificial colours or preservatives, made by Vitabiotics, UK.

Intervention 2: 250 ml of tomato soup with 20 ml olive oil. Soup will be prepared from 5 kg freshly harvested tomatoes (Harvest of Health lycopene enriched tomato), blended, and frozen down at -20 C for max 1 week. These tomatoes have been characterised previously on their lycopene content which will be determined again at Wageningen University Human Nutrition Research Unit of Wageningen University and Research.

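### Olive oil is given with the soup but not with the tablet, so the tablet-versus-soup comparison cannot separate formulation from oil, and the +10% hypothesis does not cover the tablet period as specified

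*Protocol*

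**What the plan says.** Section 8.3 of the protocol describes the two products. For the tablet: "Group A will take 40mg lycopene (2,5 pills of food supplement Vitabiotics Ultra Lycopene 15mg, potent extract". For the soup: "Group B will take 250 ml of tomato soup (matching with 40mg lycopene) with 20ml olive oil". Section 3 gives the same two regimens. Section 5.1 does so again, listing the tablets alone as Intervention 1 and then "Intervention 2: 250 ml of tomato soup with 20 ml olive oil". Nowhere does the protocol specify oil, fat, a standard meal or fasting for the tablet period, and section 5.2 leaves the normal diet unchanged.

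The question asked of this comparison is one of equal effect at equal lycopene content. Research question 2 in section 1 reads "Is a tablet lycopene with equivalent lycopene content as effective as a single dose dietary intervention regarding the change of plasma lycopene concentration". Secondary objective 1 in section 2 asks whether the tablet "provides identical plasma lycopene concentration responses compared to the dietary intervention".

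Section 1 also sets out why fat matters. It says that fat promotes absorption and that "10 gram of olive oil has been identified as an optimal dose for lycopene uptake". It notes that most experimental studies give 40 mg of lycopene by diet or "whether by pill-form (supplement), in combination with a minimum of 10 g of fat". The working hypothesis is that "a single dose response to 40 mg lycopene in combination with oil will provide a measurable response of plus 10 % in individuals", and section 4.4 repeats it as the basis for choosing 10 participants.

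**The concern.** By the protocol's own account, fat changes lycopene absorption, yet fat is supplied with only one of the two products compared. If the tablet curve is lower, the missing oil could explain it. If the curves look alike, oil may have offset a real formulation difference. Either way, the answer to secondary objective 1 and research question 2 cannot be attributed to the formulation.

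The tablet period also departs from the practice the protocol cites for pill studies, and it does not meet the condition attached to the +10% hypothesis. Section 4.4 illustrates the responder statement with intervention A. If A follows the group labels in sections 3 and 8.3, that is the tablet, so the criterion would be applied to the period without the oil on which the hypothesis depends.

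The Summary presents the comparison as tablet versus soup at equal lycopene and does not mention oil, so the asymmetry is not made part of the question there.

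**Working it through.** The protocol gives no alpha, power, standard deviation or margin, so there is no sample-size figure to reproduce. The check concerns what the design can estimate. The 40 mg stated for each product is taken at face value.

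**Inputs**
- 10 participants, 5 per sequence, AB or BA (sections 3, 4.4 and 8.2).
- A = tablet, no oil supplied; B = soup with 20 ml olive oil (sections 3, 5.1 and 8.3).
- Reference amount of olive oil: 10 g (section 1).
- Density of olive oil: 0.90 to 0.92 g/ml. This is an assumption; the protocol gives none.

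**Oil supplied**
- Soup: 20 ml × 0.90 = 18.0 g, and 20 ml × 0.92 = 18.4 g.
- Relative to the 10 g figure: 18.0/10 = 1.80 and 18.4/10 = 1.84.
- Tablet: 0 g.

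**Oil by period**

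| Sequence | Tablet periods (with oil) | Soup periods (with oil) |
|---|---|---|
| AB, n = 5 | 5 (0) | 5 (5) |
| BA, n = 5 | 5 (0) | 5 (5) |
| Total | 10 (0) | 10 (10) |

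**What the cross-over estimates.** Let π be the period effect, φ the effect of soup relative to tablet, and ω the effect of the supplied oil, with additive effects and no carry-over. The expected within-person difference, period 2 minus period 1, is:
- AB: π + (φ + ω)
- BA: π − (φ + ω)

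Half the difference between the sequences is φ + ω. The period effect cancels and the oil effect does not. Only the sum can be estimated.

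**Rank check.** The design matrix has 20 rows (10 people × 2 periods) and 13 columns: 10 for subjects and one each for period, formulation and oil. Its rank is 12. Removing the oil column leaves the rank at 12, because the oil and formulation columns are identical.

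**After the fix.** With the same oil in both periods, the differences become π + φ and π − φ. The oil term drops out, φ is estimable, and both periods meet the oil condition of the +10% hypothesis.

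**The case against.** The strongest defence is that the objective compares the tablet with the dietary intervention as the protocol defines it, and sections 3, 5.1 and 8.3 openly define that as soup with oil. Section 1 adds that equivalence may interest consumers and patients, which suggests a pragmatic comparison of a tablet as sold with a dressed soup. Any comparison of composite products mixes their components; tablet and soup also differ in food matrix and heating. Section 10 plans no statistical calculations, so no model will be fitted, and section 8.1.2 does not list the comparison among the secondary endpoints. The diary records intake on the intervention day and the two following days, and section 10 allows trends to be interpreted in the light of confounders. The intervention A sentence in section 4.4 is only an example.

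Part of this stands. The whole interventions can be compared descriptively, participants may eat fat with the tablet, and the reading of intervention A is conditional. But the remark about consumers is not a stated reason for giving oil with one product only, and the question is framed at equivalent lycopene content. Food matrix and heating belong to the difference between a tablet and a soup; oil is an addition that could be given with either. The diary records fat without equalising it, and curves drawn side by side carry the same aliasing as a fitted model.

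**Conclusion.** The concern holds. Formulation and study oil are completely aliased (10 of 10 soup periods against 0 of 10 tablet periods), with about 18 g of oil supplied on one side and none on the other. Secondary objective 1 and research question 2 cannot be answered as worded, and the +10% hypothesis does not cover the tablet period as specified.

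The limits are equally clear. The gram figures rest on the assumed density. Background fat in the tablet period is unknown, so 18 g against 0 g is the supplied contrast and not the actual difference in fat intake. Neither the size nor the direction of any net bias can be derived from the protocol. The primary question on dietary lycopene is intact in the soup period. This should be fixed before the first dosing, because the aliasing cannot be undone once the data are collected.

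**What to change.** In section 3, section 5.1 (Intervention 1) and section 8.3, give the tablets with the same 20 ml of olive oil as the soup, or give both products with the same standardised fat-containing meal.

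The cost is 10 × 20 ml = 200 ml more oil and a protocol amendment, notified to the ethics committee if it counts as substantial (section 12.3). The 10 participants, the visits and the 160 samples do not change.

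If the asymmetry is intended, three changes of wording are needed instead: restate secondary objective 1 and research question 2 as tablet without oil versus soup with oil; draw no conclusion about identical response by formulation; and limit the +10% hypothesis in sections 1 and 4.4 to the soup period.

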While the generally accepted opinion is that diets high in antioxidants are beneficial for suppressing and prevention of all cancers, and that they promote the overall health status of individuals, it may be difficult to change a life style that incorporates a healthy diet. Therefore in this study, we are searching for a parameter in body fluids that reflects the intake of healthy diet, and as such may motivate and sustain its continuous use (compliance marker). In case of prostate cancer we address lycopene as our target for reasons described above. Ideally, our lycopene related marker should reflect the short-term uptake of lycopene, and be based on a single dose consumption, in order to act as a direct feed-back to the consumers dietary action. Current methods of determination (see further) do not yet live up to point-of-care applications. There is, however, evidence that single dose consumption is reflected in the lycopene plasma concentration. In a trial in Italian consumers on lycopene kinetics on single dose consumption [5], a significant increase of plasma lycopene concentration of 40

nmol/l was observed above an individual base level (around 400 nmol/l), with a max concentration at 12 hours, and a normalisation after 48 hours after consumption of 15 mg of lycopene. Also a biomarker reflecting the adequate lycopene consumption of a medium long term (e.g. one week consumption) might provide a valuable asset for consumers. In a trial in Swiss male consumers on an 8-day intervention of 20 mg after lycopene depletion, the individual lycopene plasma concentration topped to a steady state of 1000 to 1500 nmol/l, while two weeks after the intervention (so during lycopene depletion) a plateau phase was obtained on a plasma concentration of 400-500 nmol/l [4], likely due to the release of lycopene from liver resources. We conclude that for consumer reasons the choice for a point-of-care testing of single dose lycopene is feasible, but restricted by current technology, and that feed-back on medium long term lycopene consumption is also feasible, as it is well reflected in plasma lycopene concentrations.

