3. STUDY DESIGN

Cross-over interventional pilot study.

Ten healthy individuals (male 18-75 years) are randomly divided in two groups (A and B) of 5 individuals. One week before the dietary intervention a daily food questionnaire will be completed.

One hour before the intervention a blood sample will be taken (all blood samples 6 ml EDTA plasma tube). All individuals will be given an infusion needle for 26 hours. Samples are spun and plasma is pipetted and distributed over 1 ml Eppendorf cups for immediate freezing at -80 Celsius at the research lab.

Group A will take 40 mg lycopene (2,5 pills of food supplement Vitabiotics Ultra Lycopene 15mg, potent extract). Group B will take 250 ml of tomato soup (matching with 40 mg lycopene) with 20 ml olive oil. Blood sampling as described in all individuals from needle: 1,3,6,12,24 hours after intervention, and after 48 and 72 hours by direct venapunction. Wash out period of 3 weeks, after which the identical above procedure takes place including questionnaires, but group A and B changed (cross-over). All samples (n=160) will be frozen at -80, and transported on dry ice to Wageningen University for lycopene determination.

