4.4 Sample size calculation

Observational study obtaining individual lycopene concentration curves in plasma. It is anticipated that a measurable lycopene response will be seen in all participants. Based on the literature described in the introduction section it is hypothesized that in Dutch participants the plasma level of lycopene might be comparable to the Swiss population, that a single dose response to 40mg lycopene in combination with oil will provide a measurable response of plus 10% in all individuals. Therefore a sample size of two times five participants (10 participants in total) has been chosen.

Our pilot still needs to obtain an impression that responses are observed in all individuals, and to confirm that our HPLC-assay is an adequate technique. We will express that in

percentages of the group, such as: 'In xx percent the lycopene concentration increased more than 10% of the T=0 within 48 hours after intervention A'.

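### The pilot's aim of confirming the assay rests on the share of men rising more than 10% over T0, a figure that assay error alone can produce, while the pooled duplicates that could test the assay are only monitored

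*Protocol*

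**What the plan says.** Protocol Section 4.4 gives the pilot two tasks: to see whether every man responds, and "to confirm that our HPLC-assay is an adequate technique". It says the result will be expressed as group percentages, with this model sentence: "In xx percent the lycopene concentration increased more than 10% of the T=0 within 48 hours after intervention A". The anticipated effect is the same size as the threshold: 40 mg "in combination with oil will provide a measurable response of plus 10% in all individuals".

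Section 8.3 describes the assay: an internal standard, a 30-minute run per injection, and calibration ("Concentrations are calculated using a 6-point calibration curve"). On quality control it says: "A pooled plasma sample is analyzed in duplicate in each analytical batch to monitor the quality of the analyses". It gives no CV, acceptance limit or re-run rule, and does not say how samples are assigned to batches.

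Section 3 counts the samples: "All samples (n=160) will be frozen at -80". Section 12.1 has them shipped only after all blood has been collected. Section 10 plans tables and graphs and no statistical calculations. Section 1 makes use of the marker in the patient study conditional on, among other things, the assay proving available and robust.

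**The concern.** A rise of more than 10% in one man has two possible sources: a true change in plasma lycopene, and error in the T0 or post-dose measurement. The responder percentage mixes the two. Used as evidence about the assay, it is circular: if true responses are small or absent, a less precise assay yields more apparent responders and so looks more adequate.

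The margin is thin because the anticipated response equals the threshold. The rule also favours chance findings, since any of six samples can qualify and all six are compared with a single T0.

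What is at stake is the decision to carry plasma lycopene into the study in men with prostate cancer. That decision needs a statement about assay precision, and the plan as written does not produce one.

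**Working it through.** **The plan's own figures.** 10 men × 2 periods × 8 draws = 160 samples, as stated. For the effect, Section 1 cites a single-dose study in which an increase of 40 "nmol/l was observed above an individual base level (around 400 nmol/l), with a max concentration at 12 hours"; 40/400 = 10%, which matches the anticipated response, although that study gave 15 mg. The sample size of 10 has no error rate or SD behind it, so there is nothing to reproduce.

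**Inputs.** Threshold: ratio to T0 above 1.10, so c = ln 1.10 = 0.0953. Post-dose samples within 48 hours: 1, 3, 6, 12, 24 and 48 h, so m = 6. I read the rule as met if any of the six exceeds the threshold. The CVs are assumptions, because the protocol gives none. Errors are log-normal, with σ = √ln(1 + CV²), and there is no true change.

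**All of a man's samples in one batch.** The batch effect cancels in the ratio, and

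P(false response) = 1 − ∫ φ(v) Φ(v + c/σ)⁶ dv.

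| Within-batch CV | P(false response) | Expected among 10 men | P(at least one of 10) |
|---|---|---|---|
| 2% | 0.2% | 0.02 | 2% |
| 3% | 5.6% | 0.6 | 44% |
| 3.6% | 12% | 1.2 | 73% |
| 5% | 29% | 2.9 | 97% |

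Simulation with 400,000 draws gives the same values at 2%, 3%, 5% (0.002, 0.056, 0.29) and 3.6% (about 12%).

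**T0 in a different batch from all six post-dose samples (a scenario, not a planned layout).** The T0 term then also carries the difference between two batch effects:

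P = 1 − ∫ φ(v) Φ((c + v√(σw² + 2σb²))/σw)⁶ dv.

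At within-batch CV 3%, P is 6.9%, 15% and 23% at between-batch CV 1%, 3% and 5%, against 5.6% with no batch effect. At within-batch CV 8% the split adds nothing: 52% either way.

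**Precision the 10% rule needs.** Setting P = 5% and solving for k = c/σ gives k = 3.24, so σ = 0.0953/3.24 = 0.029, a CV of about 2.9%. For a single prespecified post-dose sample the same one-sided 5% would allow 0.0953/(1.645 × √2) = 4.1%. The stricter figure comes from taking the best of six.

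**Feasibility of batching by man.** 160 × 0.5 h = 80 h of run time before calibrators and controls; 16 × 0.5 h = 8 h for one man. Shipment waits for the last sample, so grouping by man is possible.

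**The case against.** - **Batch layout and quality-control limits often sit in a laboratory manual.** This stands: silence on batch assignment is not in itself an error. The missing criterion is different, because Section 4.4 itself makes confirming the assay a task of the pilot and itself chooses how to express it. If the percentage is meant only for the responses, the assay task has no expression at all.
- **Drift may be small.** A reader might infer that between-batch drift will create false responders in this study. The documents do not support that. They give no between-batch CV and plan no layout separating T0 from post-dose samples, and they describe an internal standard and a calibration curve that may keep drift low. Several batches are likely given 80 h of runs, but not stated. Whether calibration is repeated per batch is not stated either.
- **A reader might take 10/(1.96 × √2) = 3.6% as the precision needed.** That holds for one pre/post pair. Under the any-of-six rule a CV of 3.6% still gives about 12% false responses, and an individual limit of 1.96 × √2 × CV gives about 12–15% at CVs of 3–8%.
- **The stakes are modest.** The study is a descriptive pilot, the main endpoint in Section 8.1.1 is the absolute and relative rise, full eight-point curves will be shown, and the 10% sentence is given as an example. An isolated spike can be recognised on a curve. This lowers the weight of the point but does not supply a test of the assay.

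**Conclusion.** The point holds in this form: the share of men meeting "the lycopene concentration increased more than 10% of the T=0 within 48 hours" cannot demonstrate that the assay is adequate, and the pooled duplicates that could do so have no stated role beyond monitoring. How far assay error inflates that share depends on a CV the protocol does not give: negligible at 2%, about 6% per man and intervention at 3%, and about 29% at 5%. These rates assume log-normal error, no true change, a single T0 and the any-of-six reading. They cover assay error only and leave out day-to-day variation within a man. Batch drift is a secondary and conditional risk, worth removing because doing so costs almost nothing.

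**What to change.** 1. In Section 8.3, state that all 16 samples of one man are assayed in a single batch, in random order.
2. In Sections 4.4 and 10, state that within- and between-batch CV will be computed from the pooled duplicates and reported as the test of assay adequacy, separately from the responder percentage. With one batch per man there are ten duplicate pairs, hence ten degrees of freedom for the within-batch CV, so give it with a confidence interval.
3. State that the 10% rule counts as supported only if the within-batch CV is about 2.9% or less (5% false responses per man and intervention). Otherwise either set the individual limit at about 3.2 × CV on the log scale (at CV 5%, exp(3.2 × 0.05) − 1 = 17%), or keep 10% and print the expected false-response rate beside the percentage.

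The cost is a run-order list and a small calculation from control data already being produced. If the CV proves high, the limit rises and the reported responder percentage may fall.
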